1.2 Primary Objectives

To estimate the agreement rate of detecting metastatic disease between ¹⁸F-fluciclovine-PET/CT and histopathology from radical cystectomy for detecting locoregional metastatic disease in patients with cT2-T4N0M0 muscle invasive bladder cancer by conventional CT/MRI imaging.

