13. STATISTICAL CONSIDERATIONS

13.1 Study Design, Objectives, and Endpoints

This is a prospective pilot study evaluating ¹⁸F-fluciclovine-PET/CT for detecting metastatic disease in patients with cT2-T4N0M0 muscle invasive bladder cancer.

The primary objective of this study is to estimate the agreement rate of metastatic disease status between ¹⁸F-fluciclovine-PET/CT and histopathology from radical cystectomy for detecting

locoregional metastatic disease in patients with cT2-T4N0M0 muscle invasive bladder cancer by conventional CT/MRI imaging. Secondary objectives include estimating of the rate of detection of suspected distant metastatic disease by ¹⁸F-fluciclovine-PET/CT, analysis of the association of ¹⁸F-fluciclovine uptake on PE/CT in primary bladder tumor with pathologic tumor grade/size after radical cystectomy, and analysis of ¹⁸F-fluciclovine uptake on PET/CT to the presence/absence of ASCT2 and LAT1 amino acid transporters in the resected primary bladder tumors.

The primary endpoints are metastatic disease status by ¹⁸F-fluciclovine-PET/CT and pathologic stage at radical cystectomy. The agreement rate is defined as the number of scans that are considered positive metastatic disease by both ¹⁸F-fluciclovine-PET/CT and histopathology and those considered negative metastatic disease by both ¹⁸F-fluciclovine-PET/CT and histopathology, out of all scans performed. A positive ¹⁸F-fluciclovine-PET/CT is defined as evidence of metastatic disease either regionally in the pelvic lymph nodes or distantly to bone, lungs, viscera, or lymph nodes outside of the pelvis. The ability of ¹⁸F-fluciclovine-PET/CT for detecting locoregional metastatic disease will be defined as the presence of disease detected locoregionally on ¹⁸F-fluciclovine-PET/CT. Secondary endpoints include visualization (present/absent) and number of distant metastases on ¹⁸F-fluciclovine-PET/CT. The amount of ¹⁸F-fluciclovine accumulation in the primary bladder tumor on PET will be quantified using the maximum standardized uptake value (SUVmax). Tumor grade/size and the presence of amino acid transporters will be assessed histopathologically with specimens from cystectomy as part of standard-of-care.

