13.2 Data Analysis Plan

The primary and first secondary analyses will include all 16 eligible and treated patients with completed ¹⁸F-fluciclovine-PET/CT scans and pathology dissection. Among these 16 patients, those who undergo cystectomy will be included for secondary analysis 2 and 3.

We will tabulate the metastatic disease status by ¹⁸F-fluciclovine-PET/CT (limited to bladder, locoregional nodes positive, or distant) and pathologic stage at radical cystectomy and compute the agreement rate, along with the corresponding 90% exact binomial confidence interval (CI). The proportion of patients who show positive ¹⁸F-fluciclovine-PET/CT will be computed, along with the corresponding 90% exact binomial confidence interval. This similar methodology will be used to evaluate the proportion of agreement compared to histopathology and the rates of locoregional disease and suspected distant metastatic disease detected by ¹⁸F-fluciclovine-PET/CT. In addition, treating pathologic and/or biopsy findings as the reference standard, we will estimate the sensitivity and specificity of ¹⁸F-fluciclovine-PET/CT for detection of metastatic disease.

The analysis of the relationship of ¹⁸F-fluciclovine uptake on PET/CT (SUVmax) in primary bladder tumor to pathologic tumor grade/size after radical cystectomy will be analyzed using the Kruskal-Wallis test. The Wilcoxon-Rank-Sum test will be used to assess the association between SUVmax and the presence/absence of ASCT2 and LAT1 amino acid transporters in the resected primary bladder tumors.

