13.5 Analysis of Primary Endpoints

See section 13.1

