5 WARNINGS AND PRECAUTIONS

5.1 Risk for Image Misinterpretation

Image interpretation errors can occur with Axumin PET imaging. A negative image does not rule out the presence of recurrent prostate cancer and a positive image does not confirm the presence of recurrent prostate cancer. The performance of Axumin seems to be affected by PSA levels [*See Clinical Studies (14)*]. Fluciclovine F 18 uptake is not specific for prostate cancer and may occur with other types of cancer and benign prostatic hypertrophy in primary prostate cancer. Clinical correlation, which may include histopathological evaluation of the suspected recurrence site, is recommended.

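### The plan measures locoregional detection by the scan alone (a PET-positive fraction), and no planned accuracy measure sets the pelvic-node call against nodal pathology

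*Combined protocol and SAP*

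**What the plan says.** The primary objective (1.2) is "To estimate the agreement rate of detecting metastatic disease between" PET/CT and cystectomy histopathology, for locoregional disease.

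Section 13.1 contains three relevant definitions:

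- **Agreement.** "The agreement rate is defined as the number of scans that are considered positive metastatic disease by both" PET/CT and histopathology, "and those considered negative metastatic disease by both", over all scans performed.
- **Positive scan.** A positive PET/CT "is defined as evidence of metastatic disease either regionally in the pelvic lymph nodes or distantly to bone, lungs, viscera, or lymph nodes outside" the pelvis. Nodal and distant findings both count.
- **Locoregional ability.** The ability of PET/CT "for detecting locoregional metastatic disease will be defined as the presence of disease detected locoregionally on" PET/CT. No reference standard is named.

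Section 13.2 plans the agreement rate with a 90% exact binomial interval and extends the same method to "the rates of locoregional disease and suspected distant metastatic disease detected by" PET/CT. The word *suspected* is attached to distant disease only. The section also plans sensitivity and specificity against pathology and/or biopsy, but for metastatic disease in general. It tabulates PET status in three levels (bladder only, locoregional nodes, distant) against pathologic stage.

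Section 13.5, on the primary analysis, reads only "See section 13.1".

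**The concern.** The trial asks whether the tracer finds locoregional metastases that CT/MRI missed. The one sentence in 13.1 that defines the locoregional result counts positive scans and does not ask whether they were right. Such a rate rises as specificity falls, and it cannot tell an informative reader from one who calls the same fraction positive at random.

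For distant sites an unconfirmed rate is understandable, because cystectomy does not sample them. For pelvic nodes it is unnecessary: 13.3 treats participants without pathology dissection as unevaluable and replaces them, so the reference standard is being collected.

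The planned sensitivity and specificity do not fill the gap, because a positive scan may be nodal or distant. Take a node-positive participant whose pelvic nodes are read as negative but who has a distant focus read as positive. That scan is positive under 13.1 and matches positive histology, yet the pelvic call was a miss.

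At stake is the reporting of the locoregional result: unconfirmed pelvic calls would appear as disease detected, with no matching accuracy figure beside them.

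**Working it through.** **The plan's own figures (13.3).** These rest on agreement with histopathology: continue with at least 6 of 10, succeed with at least 11 of 16, null 0.50, alternative 0.75.

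- Early stop = P(X1 ≤ 5), with n = 10 and p = 0.50, gives 0.623 (printed 0.62).
- P(success) = Σ over x1 = 6 to 10 of b(x1; 10, p) × P(X2 ≥ 11 − x1; n = 6, p). At p = 0.50 this is 0.1012 (printed 0.101). At p = 0.75 it is 0.79995 (printed 79.9%, which is the truncated value).
- The 90% exact interval for 12/16 is (0.516, 0.910) (printed 0.52, 0.91).

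The design figures hold. No figure is printed for the scan-only locoregional measure.

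**Inputs for the illustration.** Section 2.1 gives about 30% node-positive at cystectomy. Section 2.2 gives CT/MRI nodal sensitivity of 31–50% and specificity of 68–100%. The other sensitivity/specificity pairs and the 20–40% prevalence range are assumptions.

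**Formulas**, with prevalence π, sensitivity Se and specificity Sp:

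- Scan-only rate = π·Se + (1 − π)(1 − Sp). A perfect scan gives π.
- Agreement = π·Se + (1 − π)·Sp. A perfect scan gives 1.
- False-positive share of positive calls = (1 − π)(1 − Sp) / scan-only rate.

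**Results at π = 0.30**

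| Se / Sp | Scan-only rate | False-positive share | Agreement |
|---|---|---|---|
| 1.00 / 1.00 | 0.300 | 0% | 1.000 |
| 0.75 / 0.75 | 0.225 + 0.175 = 0.400 | 44% | 0.750 |
| 0.50 / 0.68 | 0.150 + 0.224 = 0.374 | 60% | 0.626 |
| 0.70 / 0.90 | 0.210 + 0.070 = 0.280 | 25% | 0.840 |
| 0.50 / 1.00 | 0.150 + 0 = 0.150 | 0% | 0.850 |

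The scan-only rate puts 0.75/0.75 above perfect and 0.50/1.00 far below it, whereas agreement ranks 0.50/1.00 above 0.75/0.75. A reader calling 37% of scans positive at random has a scan-only rate of 0.37, almost the same as 0.50/0.68.

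**When an imperfect scan exceeds a perfect one.** The condition is (1 − π)(1 − Sp) > π(1 − Se), that is, more false positives than false negatives. At π = 0.30 this needs Sp < 0.871 for Se = 0.70, Sp < 0.786 for Se = 0.50, and Sp < 0.704 for Se = 0.31.

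**Range of prevalence.** For 0.50/0.68 the rate is 0.356 at 20% prevalence (perfect 0.20) and 0.392 at 40% (perfect 0.40). The direction therefore depends on prevalence.

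**Sixteen patients, 5 node-positive**

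| Reads | Scan-only rate | Agreement | Sensitivity | Specificity |
|---|---|---|---|---|
| 5 true, 0 false positives | 5/16 = 0.313 | 16/16 | 5/5 | 11/11 |
| 3 true, 4 false positives | 7/16 = 0.438 | 10/16 = 0.625 | 3/5 | 7/11 |
| 3 true, 1 false positive | 4/16 = 0.250 | 13/16 = 0.813 | 3/5 | 10/11 |

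The last two rows have the same sensitivity. The row with more false positives shows the higher rate of disease detected.

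**The case against.** The sentence can be read as defining a per-scan variable: it follows the definition of a positive scan and speaks of presence of disease. Comparison with pathology would then come in 13.2, and a positivity rate reported beside agreement is not an error in itself. The three-level cross-tabulation against pathologic stage also supplies most of a locoregional 2×2 table. Much of this stands, but two gaps remain. The rate is still reported as locoregional disease detected, without the qualifier given to distant disease. And if the three levels are coded as exclusive categories, a scan with both pelvic and distant uptake may lose its pelvic call.

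Several stronger readings are tempting, and the documents do not support them:

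- *A mediocre scan always scores above a perfect one.* It does so only when false positives outnumber false negatives. At 30% prevalence 0.70/0.90 and 0.50/1.00 fall below 0.30.
- *The primary analysis is scan-only because 13.5 points to 13.1.* That reference covers the whole of 13.1, including the agreement definition, and a false positive lowers agreement.
- *Uptake in the bladder tumour counts as locoregional detection.* The sentence concerns metastatic disease, and 13.2 gives bladder-only findings their own level.
- *The false-positive counts in the appended label show the size of the problem.* They come from prostate cancer recurrence and need not carry over. The label's caution that "a positive image does not confirm the presence of recurrent prostate cancer" is a general warning, not an estimate for this population.

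It is also too firm to say that nodal pathology exists for everyone. Section 5.1 says cystectomy usually includes node dissection, and 13.7.2 requires only PET/CT and cystectomy for evaluability.

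**Conclusion.** The point holds as a defect in how locoregional detection is defined and labelled. The measure in 13.1 is a PET-positive fraction that false positives inflate and that does not order scans by accuracy. No planned accuracy measure isolates the pelvic-node call against nodal pathology.

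The size is illustrative. At 30% prevalence, a scan with the planned 75% agreement through sensitivity and specificity of 0.75 each would report 0.40, against 0.30 for a perfect scan, and 44% of its positive calls would be false. The prevalence is the protocol's background figure for cystectomy patients generally. The CT/MRI accuracy used for comparison need not apply to a different tracer in patients already node-negative on CT/MRI.

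No decision is affected: the agreement rate, the 6/10 and 11/16 boundaries, power and type I error rest on histopathology. The change is still worth making, because it lets the trial answer its locoregional question from data it already plans to collect.

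**What to change.** 1. **Section 13.1.** Replace the scan-only sentence with a definition such as: *Locoregional detection is assessed among participants with pelvic nodal histopathology as sensitivity (node-positive participants whose pelvic nodes are called positive on PET/CT) and specificity (node-negative participants whose pelvic nodes are called negative), each with a 90% exact confidence interval.*
2. **Section 13.2.** Rename the scan-only figure *rate of PET-suspected locoregional disease*, and report beside it the pathology-confirmed rate: true-positive pelvic calls divided by participants with nodal pathology.
3. **Data capture.** Record the pelvic-node call separately for every scan, including scans that also show distant uptake.

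The cost is wording and one recorded field. The sample size and the two-stage rule do not change. The confirmed rate can never exceed the suspected rate on the same participants and will usually be lower (0.225 against 0.400 in the 0.75/0.75 case). The sensitivity interval will be wide: 0.30 × 16 = 4.8, so about 5 node-positive patients, and 4/5 has a 90% exact interval of about 0.34 to 0.99. The report should state that imprecision openly.

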13.2 Data Analysis Plan

The primary and first secondary analyses will include all 16 eligible and treated patients with completed ¹⁸F-fluciclovine-PET/CT scans and pathology dissection. Among these 16 patients, those who undergo cystectomy will be included for secondary analysis 2 and 3.

We will tabulate the metastatic disease status by ¹⁸F-fluciclovine-PET/CT (limited to bladder, locoregional nodes positive, or distant) and pathologic stage at radical cystectomy and compute the agreement rate, along with the corresponding 90% exact binomial confidence interval (CI). The proportion of patients who show positive ¹⁸F-fluciclovine-PET/CT will be computed, along with the corresponding 90% exact binomial confidence interval. This similar methodology will be used to evaluate the proportion of agreement compared to histopathology and the rates of locoregional disease and suspected distant metastatic disease detected by ¹⁸F-fluciclovine-PET/CT. In addition, treating pathologic and/or biopsy findings as the reference standard, we will estimate the sensitivity and specificity of ¹⁸F-fluciclovine-PET/CT for detection of metastatic disease.

The analysis of the relationship of ¹⁸F-fluciclovine uptake on PET/CT (SUVmax) in primary bladder tumor to pathologic tumor grade/size after radical cystectomy will be analyzed using the Kruskal-Wallis test. The Wilcoxon-Rank-Sum test will be used to assess the association between SUVmax and the presence/absence of ASCT2 and LAT1 amino acid transporters in the resected primary bladder tumors.

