3. PARTICIPANT SELECTION

3.1 Eligibility Criteria

Participants must meet the following criteria on screening examination to be eligible to participate in the study:

- 3.1.1 Participants must have histologically or cytologically confirmed urothelial carcinoma of the bladder.
- 3.1.2 Participants must have cT2-T4N0 disease at the time of the study, as defined by conventional CT or MRI imaging. Patients must have no definite evidence of locoregional or distant metastatic disease at the time of study eligibility, as defined by conventional imaging.
- 3.1.3 Radical cystectomy must be planned for the patient after the planned ¹⁸F-fluciclovine-PET/CT.
- 3.1.4 Patients may or may not have had prior neoadjuvant therapy prior to this study.
- 3.1.5 Age ≥ 18 years. Since no dosing or adverse event data are currently available on the use of ¹⁸F-fluciclovine in participants <18 years of age, and the majority of bladder cancer occur in the adult population [42], children are excluded from this study but will be eligible for future pediatric trials.
- 3.1.6 ECOG performance status ≤ 2 (Karnofsky $\geq 60\%$, see Appendix A)
- 3.1.7 Ability and willingness to comply with the study procedures.
- 3.1.8 The effects of ¹⁸F-fluciclovine on the developing human fetus are unknown. For this reason and because radiopharmaceuticals may be teratogenic, women of childbearing potential and men must agree to use adequate contraception (barrier method of birth control; abstinence) prior to study entry and for 24 hours after the PET/CT scan is completed. Should a woman become pregnant or suspect she is pregnant while participating in this study, she should inform her treating physician immediately.
- 3.1.9 Ability to understand and the willingness to sign a written informed consent document

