5.5 Duration of Study Participation

Duration of study participation will be until the time that surgical specimens are obtained at the time of radical cystectomy.

Participants may be removed from study participation prior to the scheduled completion if one of the following events occurs:

- Unacceptable adverse event(s),
- Participant demonstrates an inability or unwillingness to comply with the study procedures,
- Participant decides to withdraw from the study,
- Condition that would result in confounding information for study procedure interpretation as determined by the study investigators,
- General or specific changes in the participant's condition render the participant unacceptable for continuing study procedures in the opinion of the treating investigator.

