5.6 Duration of Follow Up

After completing the study procedures, patients will be followed for at least 30 days. Continued standard of care will be provided by the treating physician. Participants removed from the study for unacceptable adverse events determined to be related to the study drug will be followed until resolution or stabilization of the adverse event.

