10. STUDY CALENDAR

| Phase | Pre-study | Study day | After Study |
|--|-----------|-------------------------------------|-------------|
| | | Within 6 weeks of Diagnostic CT/MRI | |
| Obtain informed consent | x | | |
| Review inclusion/exclusion criteria | x | | |
| Physical exam ¹ | x | | |
| Review of prior/concomitant medications ¹ | x | x | |
| Qualitative β -hCG | x^5 | | |
| Height/weight ² | | x | |
| ^{18}F -Fluciclovine PET/CT | | x | |
| Diagnostic CT/ MRI | x^1 | | |
| Collection of surgical specimens | | | x^6 |
| Review adverse events ⁴ | x | x | |

¹Physical exams, review of prior/concomitant medications, serum creatinine, serum or urine β -hCG at baseline, vital signs as part of the physical exam, and diagnostic CT/MRI obtained pre-study are part of the standard-of-care for patients with bladder cancer. We will be collecting and reviewing the data from these standard procedures to compare to ^{18}F -fluciclovine PET/CT imaging

results. Those with ECOG performance status ≤ 2 (Karnofsky $\geq 60\%$, see Appendix A) will be eligible. A urine pregnancy test will be performed where indicated.

²Height and weight will be obtained as part of the PET/CT scan procedures.

⁴Adverse events will be collected from the time of administration of ¹⁸F-fluciclovine until 24 hours after ¹⁸F-fluciclovine-PET/CT imaging.

⁵Female participants of childbearing potential must have a negative qualitative pregnancy test (β -hCG) at the Study Day. Results of a standard-of-care β -hCG may be used for the injection of ¹⁸F-fluciclovine if performed within 24 hours prior. Females who are two years post tubal ligation or postmenopausal for at least one year are not considered to be of childbearing potential and do not need to undergo pregnancy testing.

⁶ This is part of the standard-of-care radical cystectomy.

MEASUREMENT OF EFFECT

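### Sensitivity and specificity in 13.2 use a reference that includes biopsy, yet only surgical tissue is obtained whatever the scan shows, so distant sites would probably be verified mostly when PET is positive and any-metastasis sensitivity modestly overstated

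*Combined protocol and SAP*

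**What the plan says.** Section 13.2 plans sensitivity and specificity "for detection of metastatic disease", "treating pathologic and/or biopsy findings as the reference standard". The target is not confined to the pelvis: section 13.1 counts a scan as positive if it shows disease in the pelvic nodes or "distantly to bone, lungs, viscera, or lymph nodes outside of the pelvis". The primary objective in 1.2 is narrower and rests on "histopathology from radical cystectomy for detecting locoregional metastatic disease".

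Outside the appended package insert, this sentence of 13.2 is the only mention of biopsy. No rule says who is biopsied, at which site or when, or how an unbiopsied distant lesion is classified.

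Other sections limit where verification can come from:

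- Eligibility (3.1.2): "Patients must have no definite evidence of locoregional or distant metastatic disease at the time of study eligibility", as judged on conventional imaging.
- Study calendar (section 10): the only tissue row is "Collection of surgical specimens", at standard-of-care cystectomy. There is no biopsy row and no follow-up imaging row.
- Section 5.5: "Duration of study participation will be until the time that surgical specimens are obtained".
- Section 5.6: "patients will be followed for at least 30 days", with no imaging specified.

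Section 13.6 separately plans a sensitivity for distant metastases in comparison with standard imaging.

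**The concern.** Pelvic nodes removed at surgery are examined whatever the scan showed. Bone, lung and most visceral sites are not. Since conventional imaging gives little reason to biopsy a distant site, the usual reason would be the PET read itself. Verification of distant disease would then depend on the test being evaluated, which is partial-verification bias.

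A PET-positive distant lesion proven by biopsy enters as a true positive. A PET-negative distant metastasis in a node-negative patient is usually not found, and the patient is filed as a true negative. Any-metastasis sensitivity is pushed up and specificity slightly so. The estimate also mixes a site verified independently of the scan with sites verified mainly because of it, so it no longer answers the locoregional question in 1.2. Sensitivity and specificity are figures readers are likely to take from a diagnostic pilot.

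**Working it through.** **1. The plan's own figures.** The documents give no figure for sensitivity or specificity, so the design in 13.3 is the baseline: continue with 6 or more agreements in 10, succeed with 11 or more in 16, 50% against 75%.

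- Early stop under the null: P(X ≤ 5 | n = 10, p = 0.5) = 0.623 (stated 0.62).
- Type I error: sum over x = 6 to 10 of P(X = x | 10, 0.5) × P(Y ≥ 11 − x | 6, 0.5) = 0.1012 (stated 0.101).
- Power, same sum at p = 0.75: 0.79995 (stated 79.9%).
- 90% exact interval for 12/16: 0.516 to 0.910 (stated 0.52, 0.91).

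All reproduce. None uses the biopsy clause.

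**2. Inputs for the bias.**

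- Nodal prevalence pn = 0.30, from section 2.1 (about 30% at cystectomy); 0.25 as a variant.
- Occult distant prevalence pd = 0.05 to 0.20: assumed, not in the documents.
- PET sensitivity s = 0.4 to 0.8, the same at nodal and distant sites: assumed.
- Nodal and distant disease independent; no false-positive calls among diseased patients; distant sites verified if and only if PET-positive there; every patient keeps the dissection.

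**3. Sensitivity.**

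- Reference-positive: R = pn + (1 − pn)·pd·s
- Truly positive: T = 1 − (1 − pn)(1 − pd)
- Detected: D = pn·[1 − (1 − s)(1 − pd·s)] + (1 − pn)·pd·s
- Apparent = D/R; true = D/T. The gap in the denominators, T − R = (1 − pn)·pd·(1 − s), is the node-negative patients whose distant disease PET missed.

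Example, pn = 0.30, pd = 0.10, s = 0.4: R = 0.30 + 0.028 = 0.328; T = 1 − 0.70 × 0.90 = 0.370; D = 0.30 × (1 − 0.6 × 0.96) + 0.028 = 0.1552. Apparent 0.1552/0.328 = 0.473; true 0.1552/0.370 = 0.419.

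Apparent against true at pn = 0.30:

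| Distant prevalence | s = 0.4 | s = 0.6 | s = 0.8 |
|---|---|---|---|
| 5% | 0.438 vs 0.411 | 0.637 vs 0.611 | 0.824 vs 0.807 |
| 10% | 0.473 vs 0.419 | 0.670 vs 0.619 | 0.845 vs 0.813 |
| 20% | 0.535 vs 0.433 | 0.725 vs 0.633 | 0.878 vs 0.822 |

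The overstatement is about 2 to 10 points. At pn = 0.25 it is slightly larger; the extreme cell (pd = 0.20, s = 0.4) has R = 0.31, T = 0.40, D = 0.172, giving 0.555 against 0.430, about 12 points.

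For distant sites alone, verification only after a positive scan gives TP/(TP + 0) = 100% whatever the true sensitivity.

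**4. Specificity.** With an assumed true specificity Sp = 0.833 and missed distant cases filed as true negatives, apparent specificity = [(1 − pd)·Sp + pd·(1 − s)]/(1 − pd·s). At pd = 0.10: s = 0.4 gives (0.75 + 0.06)/0.96 = 0.844; s = 0.6 gives (0.75 + 0.04)/0.94 = 0.840. The gain is about 1 point. At pd = 0.20 and s = 0.4 it is about 2 points (0.855).

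**5. Scale in this trial.** Expected uncounted distant-only misses among 16 patients at pn = 0.30 are 16 × 0.70 × pd × (1 − s), that is 0.1 to 1.3. About 5 patients would be node-positive (0.30 × 16 = 4.8); 4/5 detected has a 90% exact interval of 0.34 to 0.99.

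**The case against.** **The biopsy trigger is inferred.** The documents never say what prompts a biopsy, and the clause could cover sampling during an altered operation (5.3). This stands as a limit on certainty. The inference is still well supported by eligibility and the calendar.

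**A reader might infer that PET-negative distant disease can never count as a miss.** That goes too far. Section 5.3 contemplates unsuspected extensive disease found at surgery, and a PET-negative patient with distant disease who is also node-positive is already a false negative. Most bone, lung and visceral disease would still escape.

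**The analysis set may blunt the effect.** Section 13.3 makes patients without pathology dissection unevaluable and replaces them. If biopsy-proven distant disease led to no dissection, which the documents do not settle, that patient would leave the analysis and could not be an added true positive. The overstatement would then be smaller.

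**A reader might also infer that specificity is materially inflated.** The calculation does not support this, and the direction is not fixed: unbiopsied PET-positive distant lesions scored as false positives would lower specificity, and the plan gives no rule for them.

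**The measure is supplementary and imprecise.** Sensitivity and specificity are not objectives in 1.2 or 1.3, and sampling error exceeds the bias. Section 13.2 also tabulates PET status by site against pathologic stage, so nodal accuracy is largely recoverable. This bears on priority. It does not justify keeping a reference rule that leans one way when a cleaner one costs little.

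**Conclusion.** The point holds for the any-metastasis sensitivity and specificity in 13.2. The stated reference verifies pelvic nodes independently of PET and distant sites probably mostly because of it. The overstatement of sensitivity is about 2 to 10 points at the protocol's nodal prevalence, and up to about 12 points in the extreme case at 25%. The effect on specificity is about 1 point or less at 10% distant prevalence. These sizes rest on assumed distant prevalence and PET sensitivity, on PET-driven biopsy, and on patients keeping their dissection.

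Two stronger readings are not supported. Accuracy confined to pelvic nodes is not biased by this route, because those nodes are examined whatever the scan shows. The Simon design and the agreement test do not depend on it either: agreement is defined against histopathology, and the biopsy clause belongs only to the sensitivity and specificity sentence. The change should be made, but the trial's main decision rule does not hang on it.

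**What to change.** - **Section 13.2:** define sensitivity and specificity as pelvic nodal PET status against lymph-node-dissection histology in the evaluable patients, and remove biopsy from that reference. Since 5.1 says cystectomy usually, not always, includes pelvic node dissection, state that only patients with node histology enter these estimates.
- **Distant lesions:** report them separately as counts: PET-suspected, biopsied, confirmed, not confirmed, unverified. Derive no sensitivity or specificity from them.
- **Section 13.6:** replace the distant-metastasis sensitivity in comparison with standard imaging by a descriptive detection rate. By eligibility that imaging shows no definite distant disease, so it supplies no definite positives. Without this edit 13.6 would contradict the revised 13.2.

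The cost is about two sentences, with no added procedure or patients. The downside is that the accuracy estimates apply to nodal disease only, remain imprecise with about five node-positive patients, and may show a lower sensitivity.
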